## **2.7.4 Other safety data**

### **2.7.4.1 ECG and cardiac imaging data**

A listing of all ECG assessments will be produced by treatment arm.

### **2.7.4.2 Vital signs**

Vital sign assessments are performed in order to characterize basic body function. The following parameters were collected: height (cm), weight (kg), body temperature ( $^{\circ}$ C), respiratory rate (breaths per minute), pulse rate (beats per minute), supine systolic and diastolic blood pressure (mmHg).

### **Data handling**

Vital signs collected on treatment will be summarized. Values measured outside of on treatment period will be flagged in the listings.

### **Data analysis**

For analysis of vital signs the clinically notable vital sign criteria are provided in [Table 2-4](#) below.

**Table 2-4 Clinically notable changes in vital signs**

Vital sign (unit)	Clinically notable criteria	
	above normal value	below normal value
Weight (kg)	increase > 10% from Baseline	decrease > 10% from Baseline
Systolic blood pressure (mmHg)	>=180 with increase from baseline of >=20	<=90 with decrease from baseline of >=20
Diastolic blood pressure (mmHg)	>=105 with increase from baseline of >=15	<=50 with decrease from baseline of >=15
Respiratory rate (bpm)	< 12	> 25
Pulse rate (bpm)	>=100 with increase from baseline of >25%	<=50 with decrease from baseline of > 25%
Body temperature	>= 39.1	-

The number and percentage of subjects with notable vital sign values (high/low) will be presented by treatment arm.

A listing of all vital sign assessments will be produced by treatment arm and notable values will be flagged. In the listing, the assessments collected outside of on-treatment period will be flagged.

#### 2.7.4.3 ECOG performance status

The performance status will be assessed according to the Eastern Cooperative Oncology Group (ECOG) performance status scale, ranging from 0 to 5, as specified in [Table 2-5](#) below.

**Table 2-5 ECOG Performance Scale**

Score	Description
0	Fully active, able to carry on all pre-disease performance without restriction
1	Restricted in physically strenuous activity but ambulatory and able to carry out work of a light or sedentary nature, e.g., light house work, office work
2	Ambulatory and capable of all self-care but unable to carry out any work activities. Up and about more than 50% of waking hours
3	Capable of only limited self-care, confined to bed or chair more than 50% of waking hours
4	Completely disabled. Cannot carry on any self-care. Totally confined to bed or chair
5	Dead

Time window for ECOG PS are defined in [Table 2-1](#). If the closest assessment to the target date has two or more ECOG filled out on the same date, then the worst ECOG PS value will be used.

Time windows are applicable for descriptive summary of ECOG data by visit only.

Frequency counts and percentages of patients in each score category will be provided by treatment arm and time point.

#### **2.7.4.4 Other safety data**

Other safety data (e.g. data relating to liver events) will be listed in the safety set.

Data from other tests will be listed, notable values will be flagged, and any other information collected will be listed as appropriate.

All assessments collected later than 130 days after the last treatment date will be flagged in the listings.

Any statistical tests performed to explore the data will be used only to identify any interesting comparisons that may warrant further consideration.

### **2.8 Secondary objective: Pharmacokinetic endpoints**

Pharmacokinetic data analyses will be performed for canakinumab and pembrolizumab concentrations. The following analyses are for canakinumab concentrations. They are also applicable and will be repeated for pembrolizumab concentrations.

PAS-canakinumab and PAS-pembrolizumab will be used in the pharmacokinetic data analysis for canakinumab and pembrolizumab concentrations, respectively.

#### **PK concentrations**

Descriptive statistics (n, m (number of non-zero concentrations), arithmetic mean, CV% mean, SD, median, geometric mean, CV% geo-mean, minimum and maximum) for canakinumab concentration will be presented at each scheduled time point for the PAS-canakinumab.

Individual concentration-time profiles for canakinumab evaluable concentrations with median will be displayed graphically for PAS-canakinumab on the semi-log view. In addition, the mean (+/- SD) and geometric mean concentration-time profiles for canakinumab over time will be displayed graphically for PAS-canakinumab on the linear and semi-log view.

All individual plasma canakinumab concentration data will be listed by treatment using the FAS.

#### **Handling of PK data below LLOQ or missing**

All concentration values below the lower limit of quantitation (LLOQ) are set to zero by the Bioanalyst, and will be displayed in the listings as zero and flagged. LLOQ values will be treated as zero in any calculations of summary statistics, and treated as missing for the calculation of the geometric means and their CV%. The number of non-zero concentrations will also be reported in the summary statistics.

Missing values for any PK data will not be imputed and will be treated as missing.

#### **Population pharmacokinetic analysis**

If there is adequate amount of data, a mixed-effects model may be applied to the serum canakinumab concentration-time data from this study along with other studies to generate post-hoc estimates of pharmacokinetic parameters using NONMEM to characterize canakinumab

[figure not shown]
exposure and to determine the effects of intrinsic (i.e. demographic factors) and extrinsic covariates (e.g. concomitant medications, formulation) on canakinumab exposure. If there is sufficient data for analysis, the details of the population pharmacokinetic analyses may be provided in a separate reporting and analysis plan, and the results may be reported in a separate population pharmacokinetic report.

## **2.9 Secondary objective: Immunogenicity**

Immunogenicity data will be summarized using the safety set. Immunogenicity will be characterized descriptively by tabulating anti-drug antibodies (ADA) prevalence at baseline and ADA incidence on-treatment. A shift table of subjects with positive or negative anti-canakinumab and anti-pembrolizumab antibodies overall and by visit will be produced (“positive” corresponds to “worst”). A listing will be provided by subject with supporting information (i.e. ADA sample status at each timepoint (including titer for positive samples) and subject ADA status). In addition, a listing will also be provided for subjects with neutralizing antibodies (NAB) testing results. Depending on the incidence of immunogenicity, additional analysis of the effect of ADA status on PK, efficacy or safety may be performed.

## **2.10 Secondary objective: Biomarkers**

As a project standard, only biomarkers collected in the clinical database will be analyzed.

There may be circumstances when a decision is made to stop sample collection, or not perform or discontinue their analysis due to either practical or strategic reasons. Under such circumstances, the number of samples may be inadequate to perform a rigorous data analysis and the available data will only be listed and potentially summarized.

Additional analyses that may be performed after the completion of the end-of-study CSR will be documented in separate reports. The data analysis will be described in an addendum of the SAP or in a stand-alone analysis plan document, as appropriate.

The FAS will be used for all biomarker analysis. Unless otherwise specified, all statistical analyses of biomarker data will be performed on patients with biomarker data.

### **Biomarker objectives**

The secondary objective related to biomarker is to assess the relationship between key blood or tissue based biomarkers and MPR.

### **List of biomarkers evaluated and the collection time points**

The biomarkers evaluated in the study are listed in [Table 2-6](#) below.

**Table 2-6      Scheduled sample biomarker summary table for secondary [REDACTED]  
objectives**

Biomarker	Time point	Sample
Key IHC (e.g., PD-L1, CD8) and other tissue immune markers	Baseline biopsy and resection	Tissue
hs-CRP	Cycle 1 Day 1 (pre-dose) Cycle 2 Day 1 (pre-dose) EOT Safety follow-up 1 Safety follow-up 3 Safety follow-up 5	Blood (serum)
Cytokine panel testing, including hs-IL-6	Cycle 1 Day 1 (pre-dose) Cycle 2 Day 1 (pre-dose) EOT Safety follow-up 1 Safety follow-up 3 (only hs-IL-6) Safety follow-up 5 (only hs-IL-6)	Blood (plasma)

**Relationship between key blood/tissue based biomarker and MPR**

The relationship between key IHC markers (PD-L1, CD8), key cytokines (hs-CRP and hs-IL-6) assessed at baseline, and MPR will be explored. MPR based on the following pre-defined baseline biomarker subgroups will be explored. The estimated and its 95% confidence interval of MPR in each subgroup, will be summarized and plotted.

- PD-L1 level (<1% vs. 1%-49% vs.  $\geq 50\%$ )
- hsCRP level (<2mg/L vs.  $\geq 2\text{mg/L}$ )
- hsCRP level (<10mg/L vs.  $\geq 10\text{mg/L}$ )
- hsCRP level (<50 mg/L vs.  $\geq 50 \text{ mg/L}$ )
- hsCRP level (<Q1 vs.  $\geq Q1$  and <Q2 vs.  $\geq Q2$  and <Q3 vs.  $\geq Q3$ )
- hs-IL-6 level (<Q1 vs.  $\geq Q1$  and <Q2 vs.  $\geq Q2$  and <Q3 vs.  $\geq Q3$ )
- CD8 level (<median vs.  $\geq \text{median}$ )
- CD8 level (<3% vs.  $\geq 3\%$ )

Quartile of the biomarker concentration is defined as:

- <Q1: <25th percentile

- $\geq Q1$  to  $<Q2$ :  $\geq 25$ th percentile and  $<50$  percentile
- $\geq Q2$  to  $<Q3$ :  $\geq 50$ th percentile and  $<75$ th percentile
- $\geq Q3$ :  $\geq 75$ th percentile

[figure not shown]
Additional cutoff might be explored if clinically indicated.

MPR will be summarized by treatment arm and subgroup along with the two-sided exact binomial 95% confidence interval ([Clopper and Pearson 1934](#)).

In addition, baseline and changes from baseline for the IHC markers and cytokines (absolute change, percent change and fold change) at each time point will be summarized by MPR status and for all subjects in tables that include sample size, mean, standard deviation, CV%, median, minimum and maximum. For fold change from baseline, geometric mean and geometric CV% will also be included.

In addition, association between MPR and time profiles of key IHC markers (PD-L1, CD8) and key cytokines (hs-CRP and hs-IL-6) will be displayed graphically by the MPR status and for all subjects.

## **2.12 Interim analysis**

Not applicable

# **3 Sample size calculation**

## **3.1 Primary analysis**

A MPR of approximately 20% can be achieved using chemotherapy (Pataer 2012 et al). A 10% absolute improvement to 30% and a 25% absolute improvement to 45% in MPR rate are considered clinically meaningful minimum improvement in canakinumab alone arm and canakinumab in combination with pembrolizumab arm, respectively.

Approximately 110 subjects will be randomized in a 2:2:1 ratio to one of the treatment arms (canakinumab alone or canakinumab in combination with pembrolizumab or pembrolizumab alone). The proof of efficacy in each treatment arm will be determined by Bayesian double criteria.

Among the 44 subjects randomized to canakinumab single agent treatment, at least 14 responders are needed to meet the proof of efficacy criteria. When the true MPR rate is  $\leq 20\%$ , the probability of erroneously declaring proof of efficacy is at most 4.4%, while the probability of declaring proof of efficacy is at least 89.8% for MPR  $\geq 40\%$  (Table 3-1).

Among the 44 subjects randomized to the canakinumab and pembrolizumab combination treatment, at least 20 responders are required to meet the proof of efficacy criteria. When the true MPR rate is  $\leq 30\%$ , the probability of erroneously declaring proof of efficacy is at most 2.1% while the probability of declaring proof of efficacy is at least 92.2% for MPR  $\geq 55\%$  (Table 3-2). Assuming an enrollment rate of 6 subjects per month, the enrollment will be completed at approximately 18 months and MPR assessment for the last patient randomized will occur at approximately 20 months from the date of first subject randomized in the study.

**Table 3-1      Operating characteristics with 44 subjects randomized to canakinumab treatment arm**

True MPR	Probability of declaring proof of efficacy (12 or more responders)	Probability of missing proof of efficacy (11 or less responders)
20%	4.4%	95.6%
30%	45.2%	54.8%

True MPR	Probability of declaring proof of efficacy (12 or more responders)	Probability of missing proof of efficacy (11 or less responders)
40%	89.8%	10.2%
50%	99.5%	0.5%

**Table 3-2 Operating characteristics with 44 subjects randomized to the canakinumab + pembrolizumab combination treatment arm**

True MPR	Probability of declaring proof of efficacy (20 or more responders)	Probability of missing proof of efficacy (19 or less responders)
30%	2.1%	97.8%
40%	27.7%	72.3%
45%	53.4%	46.6%
55%	92.2%	7.8%

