12.8 Sample size calculation

12.8.1 Primary endpoint(s)

A MPR of approximately 20% can be achieved using chemotherapy ([Pataer 2012](#)). A 10% absolute improvement to 30% and a 25% absolute improvement to 45% in MPR rate are considered clinically meaningful minimum improvement in canakinumab alone arm and canakinumab in combination with pembrolizumab arm, respectively.

Approximately 110 subjects will be randomized in a 2:2:1 ratio to one of the treatment arms (canakinumab alone or canakinumab in combination with pembrolizumab or pembrolizumab alone). The proof of efficacy in each treatment arm will be determined by Bayesian double criteria.

Among the 44 subjects randomized to canakinumab single agent treatment, at least 14 responders are needed to meet the proof of efficacy criteria. When the true MPR rate is $\leq 20\%$, the probability of erroneously declaring proof of efficacy is at most 4.4%, while the probability of declaring proof of efficacy is at least 89.8% for $\text{MPR} \geq 40\%$ ([Table 12-1](#)).

Among the 44 subjects randomized to the canakinumab and pembrolizumab combination treatment, at least 20 responders are required to meet the proof of efficacy criteria. When the true MPR rate is $\leq 30\%$, the probability of erroneously declaring proof of efficacy is at most 2.1% while the probability of declaring proof of efficacy is at least 92.2% for $\text{MPR} \geq 55\%$ ([Table 12-2](#)). Assuming an enrollment rate of 6 subjects per month, the enrollment will be completed at approximately 18 months and MPR assessment for the last patient randomized will occur at approximately 20 months from the date of first subject randomized in the study.

Table 12-1 Operating characteristics with 44 subjects randomized to canakinumab treatment arm

True MPR	Probability of declaring proof of efficacy (14 or more responders)	Probability of missing proof of efficacy (13 or less responders)
20%	4.4%	95.6%
30%	45.2%	54.8%
40%	89.8%	10.2%
50%	99.5%	0.5%

Table 12-2 Operating characteristics with 44 subjects randomized to the canakinumab + pembrolizumab combination treatment arm

True MPR	Probability of declaring proof of efficacy (20 or more responders)	Probability of missing proof of efficacy (19 or less responders)
30%	2.1%	97.8%
40%	27.7%	72.3%
45%	53.4%	46.6%
55%	92.2%	7.8%

13 Ethical considerations and administrative procedures

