## **1 Introduction**

This statistical analysis plan (SAP) describes the planned analyses for the primary clinical study report (CSR) of study CACZ885V2201C, a randomized, open-label, phase II study of canakinumab or pembrolizumab as monotherapy or in combination as neoadjuvant therapy in subjects with resectable non-small cell lung cancer.

As specified in the [Section 3](#) of study protocol, the primary analysis will be performed after all subjects have had surgical resection or have discontinued study treatment earlier due to any reason. At this time, the CSR for primary analysis will be produced. On Feb. 1, 2022, Novartis decided to halt the recruitment into the study given the number of subjects already randomized to the study and the challenges with recruitment.

No change was made to the statistical assumptions and the impact on the probability of declaring proof of efficacy (power) and the probability of missing proof of efficacy (type I error rate) will be limited. The primary analysis will be conducted as planned according to the protocol.

The content of this SAP is based on protocol CACZ885V2201C version 01 (dated 07-Apr-2020). All decisions regarding the primary analysis, as defined in the SAP document, have been made prior to database lock of the study data.

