### **Calculation of posterior probability**

The criteria for proof of efficacy are:

- the mean of the posterior distribution of MPR is at least 30% and
- the posterior probability that the MPR is  $\geq 20\%$  is at least 90%

for canakinumab single agent arm and

- the mean of the posterior distribution of MPR is at least 45% and

- the posterior probability that the MPR is  $\geq 30\%$  is at least 90% for canakinumab and pembrolizumab combination arm.

Let  $p_1$  denote the MPR rate for canakinumab single agent and follow a beta prior distribution  $\text{Beta}(a_1, b_1)$ , where  $a_1 > 0, b_1 > 0$ . Let  $y_1$  out of  $n_1$  patients reach MPR in canakinumab single agent arm. Then the posterior distribution of  $p_1$  is  $\text{Beta}(a_1 + y_1, b_1 + n_1 - y_1)$  (Spiegelhalter et al. 2004). Similarly, for canakinumab and pembrolizumab combination arm, the posterior distribution of  $p_2$  is  $\text{Beta}(a_2 + y_2, b_2 + n_2 - y_2)$ .

A minimally informative unimodal Beta prior (Neuenschwander et al. 2008) will be used. For canakinumab single agent arm, the parameters will be chosen so that the mean of the prior distribution is equal to 0.3, which corresponds to  $\text{Beta}(3/7, 1)$ . For canakinumab in combination with pembrolizumab arm, the parameters will be chosen so that the median of the prior distribution is equal to 0.45, which corresponds to  $\text{Beta}(9/11, 1)$ .

The efficacy criteria will be assessed based on the actual number of patients enrolled. For example, if the total number of patients in canakinumab is 44, the first efficacy criterion requires that at least 14 patients who are MPR responders. In that case, the posterior distribution is  $\text{Beta}(3/7 + 14, 1 + 44 - 14)$  and the posterior probability  $P(\text{MPR rate} \geq 0.2) = 96.5\%$ .

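### SAP Table 3-1 labels the canakinumab-alone success threshold as 12 of 44 responders; its own probabilities, the SAP text and the protocol are all for 14 of 44

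*SAP*

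**What the plan says.** SAP Table 3-1 is titled for 44 subjects randomized to canakinumab alone. Its two probability columns are headed "Probability of declaring proof of efficacy (12 or more responders") and "Probability of missing proof of efficacy (11 or less responders"), and the headers are repeated where the table is split.

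Three other places state the threshold for the same arm and the same number of subjects:

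- SAP 3.1, which refers the reader to Table 3-1, says that "at least 14 responders are needed to meet the proof of efficacy criteria".
- SAP 5.4.1, in its worked example for 44 subjects, says that "the first efficacy criterion requires that at least 14 patients who are MPR responders".
- Protocol 12.8.1, Table 12-1, heads the corresponding column "Probability of declaring proof of efficacy (14 or more responders"), with 13 or fewer in the other column. Its eight probabilities are the same as those in SAP Table 3-1.

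The rule that decides success is in SAP 2.5.2 and 5.4.1: posterior mean MPR of at least 30%, and posterior probability of at least 90% that MPR is 20% or more, under a Beta(3/7, 1) prior. SAP 5.4.1 adds that "The efficacy criteria will be assessed based on the actual number of patients enrolled". SAP 1 records that the sponsor "decided to halt the recruitment into the study given the number of subjects already randomized".

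**The concern.** For one of the two primary arms, the SAP gives two different minimum responder counts at the same sample size. A reader who uses Table 3-1 to find the bar for success finds 12; one who reads the paragraph before it finds 14.

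The recruitment halt makes the discrepancy easier to misread. The required count falls with the arm size, and 12 is a plausible count for an arm somewhat smaller than 44. The header could be taken for an intended revision after the halt, although the title and all the probabilities still refer to 44. If 12 of 44 were applied as the rule, results that fail the stated Bayesian criteria would be called a success.

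**Working it through.** **Inputs.** n = 44 (title of SAP Table 3-1); candidate thresholds 12 (table header) and 14 (SAP 3.1, SAP 5.4.1, protocol Table 12-1); prior Beta(3/7, 1) and the two posterior criteria (SAP 2.5.2, 5.4.1); true MPR values 20, 30, 40 and 50% (Table 3-1).

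**Step 1: which threshold do the printed probabilities belong to?** With X ~ Binomial(44, p), the probability of declaring efficacy at threshold r is P(X ≥ r).

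| Threshold | p = 20% | 30% | 40% | 50% |
|---|---|---|---|---|
| Printed in Table 3-1 | 4.4% | 45.2% | 89.8% | 99.5% |
| r = 14 | 4.36% | 45.21% | 89.79% | 99.52% |
| r = 13 | 8.58% | 58.27% | 94.41% | 99.82% |
| r = 12 (header) | 15.42% | 70.64% | 97.23% | 99.94% |

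Only r = 14 reproduces the printed row. The second column is the complement. For 13 or fewer the values are 95.64, 54.79, 10.21 and 0.48%, matching the printed 95.6, 54.8, 10.2 and 0.5%. For 11 or fewer, as headed, they would be 84.6, 29.4, 2.8 and 0.1%.

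**Step 2: what does the decision rule require at n = 44?** With y responders the posterior is Beta(3/7 + y, 1 + 44 − y), whose mean is (3/7 + y)/(44 + 10/7).

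| y | Posterior mean | P(MPR ≥ 20%) | Result |
|---|---|---|---|
| 12 | 27.4% | 87.2% | both criteria fail |
| 13 | 29.6% | 93.0% | mean criterion fails |
| 14 | 31.8% | 96.5% | both met |

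The minimum is 14, and the 96.5% quoted in SAP 5.4.1 is reproduced.

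**Step 3: could 12 be an update for a smaller arm?** The prior mean is 0.30, so the mean criterion reduces to a simple form. (3/7 + y)/(n + 10/7) ≥ 0.30 gives y ≥ 0.30n + 3/7 − 3/7 = 0.30n. The smallest whole y is therefore 11 at n = 36 (0.30n = 10.8), 12 at n = 37 to 40 (11.1 to 12.0), 13 at n = 41 to 43 (12.3 to 12.9) and 14 at n = 44 (13.2). The probability criterion is also met at each of these counts; for example, it is 93.0% at 12 of 40.

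So 12 is the correct threshold for 37 to 40 subjects. The documents do not give the final arm size, so this range is an assumption. P(X ≥ 12) at the four true rates then runs from 5.2, 43.4, 86.7 and 99.0% (n = 37) to 8.8, 55.9, 92.9 and 99.7% (n = 40). No n in that range gives the printed row, so the table as it stands is not a re-based one.

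**The case against.** The strongest counter-argument is that nothing in the analysis uses the header. The decision is made on the posterior mean and posterior probability at the number actually enrolled, with the prior fixed numerically. No estimate, interval or conclusion depends on the responder count in a planning table. The paragraph immediately before the table gives 14 with the same 4.4% and 89.8%, and the worked example and the protocol agree, so a careful reader can resolve the conflict. On this view it is an editorial slip, the 15.4% false-positive probability is hypothetical, and the post-halt misreading is speculative because the arm size is not stated.

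Most of this stands. The planned error rates do not change, and 15.4% would arise only if the header replaced the stated criteria, which no passage instructs. It does not remove the error, however. The figure is wrong as written, it concerns the success threshold of a primary arm, and it sits in the table that SAP 3.1 cites for that arm's operating characteristics. The post-halt reading is not needed to show the error; it only explains why the header might go unquestioned.

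**Conclusion.** The concern holds. The headers of SAP Table 3-1 are wrong by two responders: 14 or more and 13 or less are correct at n = 44. The eight probabilities, the table title, the SAP 3.1 text, the worked example and the posterior criteria for this arm are all consistent with 14.

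The false-positive probability at a true MPR of 20% remains 4.4%, and the probability of success at 40% remains 89.8%. Taken literally, the headers would imply 15.4% and 97.2%. This conclusion uses only the documents' own n, prior and criteria; the one assumption, an arm of 37 to 40 subjects, enters only in explaining how the header could be misread. It should be fixed as a misstated threshold. It is not a flaw in the design.

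**What to change.** Change the Table 3-1 headers to 14 or more responders and 13 or less responders, in both parts of the split table. This is a wording change to the SAP only.

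If the sponsor would rather show the table at the actual arm size after the recruitment halt, the title, the threshold and all eight probabilities must be recomputed together. That is optional, since SAP 5.4.1 already applies the criteria to actual enrolment.

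A separate minor wording point can be corrected in the same edit. For the combination arm, SAP 5.4.1 says "the parameters will be chosen so that the median of the prior distribution is equal to 0.45" and gives Beta(9/11, 1). That distribution has mean (9/11)/(9/11 + 1) = 0.45 and median 0.5^(11/9) = 0.429, so the word should be mean. The prior is stated numerically, so no result changes.
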